#### **Intake and Consent Process:**

##### **For MUSC Charleston patients:**

If the electronic medical record identifies them as a smoker, or if they report being a smoker at the time of their scan, they will meet or speak by phone with one of our study research assistants. Patients who express interest in the study will set up an intake appointment with a research staff member within 60 days of the date of their shared decision making visit. Patients who decline to participate in the study will be asked why and will be asked if we can collect basic demographic data from their medical record (e.g., age, gender, race, ethnicity, pack years). All eligible lung cancer screening patients will receive a postcard prior to their appointment informing them that they may be eligible to participate in a research study. The study staff will call these patients prior to their appointment to gauge interest in the study. If the patient would like more information, a study staff member will either meet the patient at the scanner on their proposed scan date, at another agreed upon time and place, or speak by phone. If the patient is interested in enrolling or getting more information about the study, a research assistant will speak to them or set a date with the patient to enroll them into the study. Study eligibility will be determined in concert with a clinic staff member and the site PI ([name] at MUSC or [name] at Yale) following completion of baseline assessments, a review of the electronic medical record for health information (if necessary), and the eligibility checklist.

Informed consent will be obtained prior to any other procedures. We will provide participants with the option to complete consent and/or baseline session 1) in person, 2) via an MUSC approved HIPAA compliant video

**Commented [TB1]:** [name], would you please frame this to the IRB like this:

We chose to change our inclusion of potential participants from the day of the scan to the day of the shared decision making visit because although these 2 events generally occur on the same date, it is possible that patients may engage in a shared decision making visit and decline participation in the scan. We feel this is an important population to include in the study.

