If a patient, using the remote study visit option, is randomized into a group receiving NRT, the medications will be mailed to the participant as soon as possible. If a patient is randomized into the gain-framed group, they will be asked to view the gain-framed video via an emailed or texted link and the gain-framed materials will be mailed to them as soon as possible. Following the consent process, patients will also be asked to complete the baseline assessments during their first meeting. If they are unable to complete these during this appointment, research staff will remind them to complete these assessments within a week. Additionally, after consent has been obtained and eligibility has been established, we will offer participants the option to complete the baseline assessments at another time (including by phone) within a week of the start of the intake session to allow for greater flexibility to accommodate participant schedules. The study visit will be done at the clinic, at a public location convenient for the participant, or via phone. Participants will be paid \$50 for completion of all intake assessments.

For MUSC Lancaster, MUSC Chester, MUSC Florence, and MUSC Columbia patients:

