strategy involving a gain-framed intervention + 2 weeks of nicotine patches and lozenges compared to a strategy of an unframed behavioral intervention + no medication. Primary and secondary models will be developed including the effects of both randomized conditions; gain framed vs. unframed messaging and NRT vs. no medication, and a cluster effect of study site. Models will be computed both unadjusted and adjusted for significant covariates found in the preliminary analysis. For these efficacy analyses, 7-day point prevalence abstinence will be defined as having no cigarettes (or other tobacco products) for 7 days, confirmed by CO breath test less than or equal to 10 ppm. All randomized participants will be included in the analyses (intent-to-treat approach), and participants will be considered non-abstinent at any missed visit (drop-out/lost-to-follow-up included). To comprehensively analyze the longitudinal efficacy of gain framed messages and NRT sampling, the entire study time course will be analyzed with repeated measures logistic regression using a Generalized Estimating Equation framework. Continuous abstinence (CA) from the time of lung screening to the 1 and 3 month follow-ups (Weeks 4 and 12) and to final follow-up visit (Week 26) will be assessed using logistic regression analysis. Time to first lapse (puff) and time to relapse (first of 3 consecutive days smoking  $\geq 1$  cigarette) will be analyzed using Cox Proportional Hazard models with effects of both randomized conditions in a 2x2 design; gain framed vs. unframed messaging and NRT vs. no medication, and a cluster effect of study site. In addition to the primary intent-to-treat analyses, additional exploratory approaches (e.g., modified intent-to-treat models, per protocol analysis, and completer analysis) will be undertaken as indicated and a sensitivity analysis comparing these models to the ITT model will be completed.

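### Continuous abstinence is counted from lung screening, although randomisation may follow weeks later, so smoking before any intervention is scored as failure

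*Combined protocol and SAP*

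**What the plan says.** All references are to the combined protocol and SAP.

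- **Start of the outcome.** Statistical Analysis defines "Continuous abstinence (CA) from the time of lung screening to the 1 and 3 month follow-ups (Weeks 4 and 12", with a further assessment at the final visit (Week 26), by logistic regression. The analysis set is stated just before: "All randomized participants will be included in the analyses (intent-to-treat approach".
- **Randomisation.** Under Standard Care for Smoking Cessation Advice, randomisation takes place upon consent.
- **Intake at MUSC.** In the section for MUSC Charleston patients, interested patients set up an "intake appointment with a research staff member within 60 days of the date of their shared decision making visit". The section for the Lancaster, Chester, Florence and Columbia sites gives the same 60 days. A margin comment in the Charleston section says of the decision visit and the scan that "although these 2 events generally occur on the same date".
- **Intake at the VA.** Medication Dispersal for patients at the VA provides for intake on a later day than the screening visit and sets no maximum gap. I found no separate window for Yale.
- **Scan decliners.** The same margin comment explains that the reference date was moved from the scan to the decision visit because "it is possible that patients may engage in a shared decision making visit and decline participation in the scan", and calls such patients an important group to include.
- **Smoking criterion and records.** Participants must have smoked within the preceding 30 days (Participants). The Timeline Followback calendar covers 30 days before treatment and then each day through the 6 months of the study (Assessments).
- **A conflicting description.** Sources of Materials, under Protection of Human Subjects, equates intake with the lung cancer screening appointment.

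**The concern.** An outcome that measures the effect of a randomised intervention should not be decided before randomisation. Here the clock can start days or weeks before the participant has consented, been allocated or received anything. A participant who goes on smoking in that interval, as a current smoker ordinarily would, has already failed when the intervention begins, whatever happens afterwards.

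Three things are at stake for this secondary outcome. Some participants can contribute only failures. Some may have no usable start date. For some, the smoking record needed to apply the definition is not collected. The analyst would then have to choose a start date (scan, decision visit or randomisation) after the data exist, and each choice gives a different outcome variable.

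**Working it through.** The plan gives no rate, sample size or power for continuous abstinence, so there is no figure to reproduce. The check is date arithmetic on the plan's own windows.

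**Inputs.** Intake up to 60 days after the decision visit (MUSC); smoking criterion 30 days; calendar look-back 30 days; Week 26 = 26 × 7 = 182 days. Let s be the days from decision visit to scan, and g the days from scan to intake.

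**1. Longest pre-randomisation interval.** The largest g is 60 − s. With a same-day scan (s = 0) it is 60 days. All of it lies inside the continuous-abstinence period and before any intervention.

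**2. Certain failures.** Suppose the 30-day smoking criterion is applied at intake. If g is more than 30, the qualifying cigarette was smoked after the scan, so continuous abstinence has already failed. The intake days on which this is certain number max(0, 30 − s):

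| s (days) | Latest intake after scan | Certain-failure days |
|---|---|---|
| 0 | 60 | 30 (days 31 to 60) |
| 14 | 46 | 16 (days 31 to 46) |
| 30 or more | 30 or fewer | 0 |

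Applying the criterion at intake is the natural reading but is not explicit. The Charleston section settles eligibility "following completion of baseline assessments, a review of the electronic medical record for health information (if necessary), and the eligibility checklist", and its text on remote visits speaks of baseline assessments being offered "after consent has been obtained and eligibility has been established"; both place the decision at or after consent. Smokers are, however, first identified from the record "or if they report being a smoker at the time of their scan". If the criterion is applied then, failure before randomisation is likely but not certain.

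**3. Unrecorded days.** If treatment starts at intake, the calendar reaches back 30 days, so max(0, g − 30) days after the scan are not covered: 15 days at g = 45 and 30 days at g = 60.

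**4. Unequal periods.** The Follow-up section does not say from which date the 1-, 3- and 6-month visits run. If they run from intake, abstinence from screening to Week 26 spans 182 + g days, up to 182 + 60 = 242.

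**5. Reverse order.** If the scan comes after randomisation, the rule errs the other way: smoking after randomisation but before the scan is not counted.

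**6. Effect on the comparison.** Suppose a share f of each arm fails before randomisation, unrelated to what their outcome would have been. Each arm's rate p becomes p(1 − f). The risk difference shrinks by the factor 1 − f, the risk ratio is unchanged, and the odds ratio moves slightly towards it. The illustration below rests on assumptions only. It uses 367/2 = 183.5 per arm, a two-sided 5% test and the normal approximation with pooled variance under the null. The first pair of rates is assumed; the second borrows the plan's point-prevalence rates, which are not continuous-abstinence rates.

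| Rates | f | Difference (points) | Odds ratio | Power |
|---|---|---|---|---|
| 12% vs 6% | 0 | 6.0 | 2.14 | 52% |
| | 10% | 5.4 | 2.12 | 47% |
| | 25% | 4.5 | 2.10 | 40% |
| 28% vs 13% | 0 | 15.0 | 2.60 | 95% |
| | 10% | 13.5 | 2.54 | 92% |
| | 25% | 11.25 | 2.46 | 85% |

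The values of f are also assumed.

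**The case against.** The strongest reply is that 60 days is an outer limit and the plan expects most intakes to be close to screening. Staff call before the appointment and may meet the patient at the scanner; the VA text treats a later intake as the exception; Sources of Materials equates intake with the screening appointment. The outcome is secondary, the misclassification is unrelated to arm, and the odds ratio hardly moves. All of this stands. It limits the size of the problem, but it does not make the stated rule right for those enrolled later.

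Four stronger readings are tempting and should not be adopted:

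- **Week 4 could fall before randomisation.** A reader might infer this by counting Week 4 (day 28) from the scan. The reading is strained, because Statistical Analysis ties Weeks 4, 12 and 26 to follow-up visits, which only enrolled participants attend.
- **Scan decliners definitely have no start date.** This holds only if lung screening means the scan. The sample message under Gain-Framed Messaging mentions attending a lung screening visit and also allows for a person who then decides against screening. On that usage a decliner has a visit date. The plan does not say which meaning applies.
- **A definite loss of power.** The illustration needs a share affected and continuous-abstinence rates, and the documents give neither.
- **Starting at randomisation cures everything.** It does not. Remote participants receive materials by post after randomisation, participants are only encouraged to set a quit date, and the NRT sampling rationale disclaims any expectation of quitting at once. Without a grace period, smoking in those days still counts as failure.

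**Conclusion.** The concern holds in limited form. For continuous abstinence, the stated start conflicts with the intake and randomisation procedures. Following it scores smoking before randomisation as treatment failure, and can require smoking data from outside the calendar's look-back. This is a rule that gives the wrong result, not merely a missing detail.

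With a same-day scan, up to 60 days before randomisation count towards the outcome. If the smoking criterion is applied at intake, failure is certain for intakes on days 31 to 60. A scan later than the decision visit narrows that range and removes it at 30 days or more. Up to 30 days after the scan can be unrecorded.

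The effect favours neither arm. It dilutes the absolute difference and costs some power, by an amount that cannot be computed from the documents.

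A reader might infer that the primary outcome is compromised in the same way. It is not: 7-day point prevalence at the 6-month visit does not look back to the time before randomisation. Its timing is described both as six months after screening (Hypothesis 1) and as the 6-month follow-up visit (Power and Sample size), which is a matter of stating the visit origin.

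**What to change.** In Statistical Analysis, define continuous abstinence from the date of randomisation for all randomised participants, including those who decline the scan, to the 1-, 3- and 6-month visits, derived from the daily Timeline Followback calendar. State whether a grace period applies for smoking after randomisation but before a quit date or the arrival of mailed materials.

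Reconcile Sources of Materials, which equates intake with the screening appointment, with the MUSC intake sections and the VA medication section. State in Follow-up the origin from which visits are in fact scheduled. Do not re-date visits already made; the plan is at Version 13, and changing the schedule or the date of the primary outcome would be more than a wording change.

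The new definition needs no added data collection, because the calendar already records daily use over follow-up. The cost is that continuous abstinence is no longer anchored to the screening event, which is a small loss.

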**Gain-framed messages and NRT for lung cancer screening patients ( Pro00055397 )**  
**PI: [name]**  
**Version 13 (11/14/2022)**

**SPECIFIC AIMS**

Screening for lung cancer at earlier, more treatable stages has the potential to reduce mortality from the US's most deadly cancer. The US Preventive Services Task Force (USPSTF) now recommends annual screening for lung cancer with low-dose computed tomography (LDCT) for high risk individuals based on age and smoking history. The Center for Medicare and Medicaid Services (CMS) recently approved annual lung cancer screening for its beneficiaries when conducted in centers offering comprehensive programs that include advice on smoking cessation. While it has been suggested that LC screening is a potential teachable moment, most current smokers seen for screening have variable motivation to quit, and many are unwilling to engage in a formal cessation program. Thus, there is a strong need to address smoking cessation across this continuum, catalyzing treatment engagement and cessation among all. The interventions in this study are broad and translational – effectively promoting quitting among all smokers and doing so in a way that is easily disseminable. In the context of 3 lung cancer screening programs (MUSC, VA and Yale) this project will evaluate a more intense yet still feasible intervention to enhance patient motivation to make and succeed in a quit attempt.

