increasing intentions to quit, quit attempts, and smoking cessation in general populations of smokers. Thus, the primary hypothesis for our message framing intervention is that *gain-framed messages are especially persuasive when promoting cancer prevention behaviors like smoking cessation, and thus can be utilized to further improve standard tobacco cessation counseling in the context of lung cancer screening.* We also believe that gain-framed messaging will have a particularly salient effect when presented in conjunction with a concrete, behaviorally-based cue to action as is offered through NRT sampling.

**Nicotine Replacement Therapy (NRT) Sampling** NRT sampling merely refers to providing short, starter packets of NRT, which can be easily added to existing counseling (message framing) protocols. Sampling is distinct from a full course of NRT treatment, in that the intent is to engage smokers in the process of quitting, but without any requirement or expectation to quit immediately and/or abruptly. It is a softer, gradual exposure to the quitting process that is conceptually designed to heighten smoker acceptance and enhance motivation and self-confidence. It is also rooted in marketing research (businesses have been doing this for years), which shows that brief exposure to a product, when provided for free, increases positive opinion and more importantly increases further use of that product.

There are several mechanisms by which gain-framed messages and NRT sampling, when offered in conjunction with lung cancer screening, could promote downstream changes in smoking behavior (quit attempts, abstinence; see **Figure 1**). We discuss these potential mediators for both interventions below. One is through improved self-efficacy. As smokers gain confidence in controlling smoking, they may be more likely to believe that total abstinence is possible. Changes in outcome expectancies have been shown to act as a mediator in our

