### **Design and Methods:**

#### **General overview:**

We propose a group comparison study (gain-framed intervention vs. unframed intervention, starter package of 2 weeks of nicotine patches and lozenges vs. no medication) to evaluation methods to boost rates of smoking cessation for a high-risk group of smokers (N=367) with varying levels of motivation across 3 study sites (MUSC, Ralph H. Johnson Veteran Administration and Yale). All eligible study participants will be randomized to receive either: 1) Unframed Messaging (hereafter referred to as UM) with no medication, or 2) Gain-framed Messaging + Meds (i.e., 1 gain-framed video and print materials + 2 week starter pack of NRT; hereafter referred to as GM+M).

**Participants:** Our target sample will be 367 lung screening patients who currently smoke at each of 3 study sites: MUSC), Ralph Johnson VA, and Yale Cancer Center); Total N=367. The following eligibility criteria will ensure that we obtain our study sample of lung screening patients. **Inclusion:** 1) 50 years or older (we see no reason for an upper limit given supportive evidence for cessation among elderly), 2) at least a 20 pack year history of smoking (i.e., the base population of high risk smokers to get screened) as assessed by the patients ordering healthcare provider or the research team, 3) current smoker (defined as any smoking in the past 30 days – this is the criteria our lung cancer screening programs will use to trigger tobacco treatment interventions), 4) willing to be randomized, 5) English speaking; **Exclusion:** 1) unstable psychiatric/medical conditions such as suicidal ideation, acute psychosis, severe alcohol dependence, or dementia, and 2) known allergy to adhesives, and 3) current participation in another tobacco treatment program (e.g., using medication from a primary care doctor, quitline, etc).

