#### Standard Care for Smoking Cessation Advice for All Study Participants:

Upon consent, all participants will be randomized to study group, stratified by study site and level of motivation (low: 0-7 on VAS ladder vs. 8-10). Following randomization, all participants will receive a bag with small smoking cessation tools (i.e., stress ball) and smoking cessation handouts based on practical counseling principles, which is a cognitive-behavioral, evidence-based, smoking cessation treatment modality focused on specific strategies to support quitting smoking. If patients are meeting with research staff via tele-consent, e-consent, or by mail, the wellness bag will be mailed to them with the intervention materials they were randomized to receive. All participants will be encouraged to set a quit date.

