Keep your phone charged and on your person at all times in case of emergency

To ensure the safety and privacy of the MUSC participant:

We will try to meet in a public location that has an area that is in clear sight of others but semi-private area where we can obtain research data as confidentially as possible.

We will not use the patient's name in public at this location.

We will speak in low volume to communicate with the participant as not to share information with those in the surrounding area.

To ensure the safety and privacy of the VA participant:

We create a VA REDCap database behind the VA firewall where all participant study data will be collected, stored and analyzed.

Assessments (Items with an asterisk will be tested as a mediator or moderator):

Demographic and Smoking History Questionnaire: As in our previous studies, this questionnaire will obtain: 1) basic demographic information and 2) basic smoking status and history. At baseline this will assess basic smoking status and history which will allow us to personalize the messages for participants in the study groups receiving gain-framed messages.

Tobacco and Alcohol Use Calendar (Timeline Followback): This standardized, validated, and reliable experimenter-administered rating scale will be used to obtain quantity and frequency estimates of cigarette consumption for a 30-day period prior to treatment. As in our previous clinical trials, we will use the calendar to record tobacco use on a daily basis throughout the 6 months of the study.

Abstinence: For our primary outcome, consistent with our past clinical trials, abstinence will be defined as 7-day point prevalence abstinence, meaning no cigarettes (or other tobacco products) for 7 days, confirmed by CO breath test less than or equal to 10 ppm.

CO levels: Expired breath CO will be monitored at each in-person visit to verify abstinence during treatment. Levels of CO will be measured using a Bedfont Micro+ Smokerlyzer Monitor (Innovative Medical Marketing, Williamsburg, VA), which is a precision instrument for detecting CO in exhaled breath. Both study sites are currently using these devices and have several on hand. If smoking status is verified remotely, participants will be mailed a Bedfont iCO Smokerlyzer with instructions for use. They will complete the breath test live on a HIPAA compliant video platform and results will be emailed to study staff.

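### Continuous abstinence is counted from lung screening with no grace period, so participants who quit later and stay quit are scored as failures at Weeks 4, 12 and 26

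*Combined protocol and SAP*

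**What the plan says.** Statistical Analysis defines the secondary outcomes as "Continuous abstinence (CA) from the time of lung screening to the 1 and 3 month follow-ups (Weeks 4 and 12") and to the final visit at Week 26, each analysed by logistic regression. No grace period, quit-date anchor or permitted slip is stated.

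Other sections describe an intervention that does not ask for quitting on the first day:

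- The NRT sampling paragraph under Significance says that sampling engages smokers "without any requirement or expectation to quit immediately and/or abruptly".
- The standard-care section says "All participants will be encouraged to set a quit date". This comes after consent and randomisation, and no timing is given.
- The intake section for MUSC Charleston sets the intake appointment "within 60 days of the date of their shared decision making visit". Remote participants are mailed their NRT after randomisation, and the Lancaster, Chester, Florence and Columbia sites are wholly remote.
- Eligibility requires a "current smoker (defined as any smoking in the past 30 days").

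Continuous abstinence is not the primary outcome: "For our primary outcome, consistent with our past clinical trials, abstinence will be defined as 7-day point prevalence abstinence", CO-confirmed and tested at 6 months. Daily smoking data will exist, because the Timeline Followback entry says "we will use the calendar to record tobacco use on a daily basis throughout the 6 months of the study".

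**The concern.** The outcome's clock and the intervention's clock do not match. Continuous abstinence starts at screening. Randomisation, the quit-date advice and the NRT come later, in some cases weeks later. A participant who samples NRT, quits two weeks after receiving it and never smokes again is a failure at Week 4, Week 12 and Week 26.

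Continuous abstinence is the only proportion in the plan that speaks to sustained quitting. If it mostly records who stopped at once, a null result could be misread as absence of a lasting effect. If sampling leads people to quit later than controls do, the outcome could also be tilted against the intervention arm.

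**Working it through.** **Step 1: can the clock start before the intervention?** Yes. The intake section allows up to 60 days between the shared decision making visit and intake, and a comment in that section says the visit and the scan generally fall on the same date. Take a participant whose visit and scan coincide and who enrols more than 30 days later. Eligibility requires smoking in the 30 days before enrolment, so that smoking falls after screening and the participant has already failed before being randomised. The same comment says that patients who decline the scan are to be included; they have no scan date from which to count.

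**Step 2: does moving the start to randomisation cure it?** Only in part. Remote participants cannot have the mailed NRT on the day of randomisation, and nobody is asked to quit that day. A delayed quitter still fails all three time points.

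**Step 3: reproduce the plan's own figure.** Inputs from Power and Sample size: 28% vs 13% 7-day point prevalence at 6 months, type 1 error 5% (two-sided assumed), power 80%, 123 per group. The two-proportion formula gives 113 per group uncorrected and 126 with continuity correction, so 123 is reproduced closely. Uncorrected power at 123 per group is 83.4%.

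**Step 4: power for strict continuous abstinence at Week 26.** The plan gives no continuous-abstinence rate and no distribution of quit dates. I assume that a share f of the planned 6-month abstainers meets the strict definition, the same in both arms, with 367 participants split equally (183.5 per arm; the ratio is not stated explicitly).

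Rates: p1 = f × 0.28, p0 = f × 0.13, with pbar their mean.

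Power = Φ[(p1 − p0 − 1.96 × SE0) / SE1], where SE0 = √(2 × pbar × (1 − pbar) / n) and SE1 = √((p0(1 − p0) + p1(1 − p1)) / n).

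- f = 1: SE0 = 0.0422, SE1 = 0.0414; (0.150 − 0.0826) / 0.0414 = 1.63; power 94.8%.
- f = 0.5: SE0 = 0.0317, SE1 = 0.0314; (0.075 − 0.0621) / 0.0314 = 0.41; power 66.0%.

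| f | Rates | Power, 183.5 per arm | Power, 146.8 per arm (367 less 20%) |
|---|---|---|---|
| 1.0 | 28% vs 13% | 95% | 89% |
| 0.75 | 21% vs 9.8% | 85% | 76% |
| 0.5 | 14% vs 6.5% | 66% | 56% |
| 0.3 | 8.4% vs 3.9% | 43% | 36% |
| 0.2 | 5.6% vs 2.6% | 30% | 25% |
| 0.1 | 2.8% vs 1.3% | 17% | 15% |

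At 183.5 per arm, power drops below 80% when f is under about 0.67, and below half its full value when f is under about 0.33.

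**Step 5: unequal delay.** If f is 0.25 in the sampling arm and 0.5 in control (assumed), the rates are 0.25 × 28% = 7.0% and 0.5 × 13% = 6.5%. Power to show a benefit is about 4%. With f of 0.4 and 0.5, the rates are 11.2% and 6.5% and power is 35%.

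**Limits of the arithmetic.** It applies to Week 26 only, because the plan gives no expected rates for Weeks 4 and 12. Also, f falls for two reasons: delayed quitting and lapses later in follow-up. A grace period recovers only the first, so the gap between rows is not the gain to expect from the fix.

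**The case against.** Four points can be made for the plan.

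*The main results do not depend on this outcome.* This stands. CO-confirmed 7-day point prevalence at 6 months credits a delayed quitter who is abstinent then, and the GEE analysis of the whole time course picks up late quitting. Specific Aims also promises several definitions of success. A null continuous-abstinence result would be read beside these. They do not measure sustained abstinence, however, and no further definition is named there.

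*The power loss is not established.* This also stands. A reader might infer that the outcome loses most of its power or could not detect a sustained effect. The documents do not support either: they claim no power for continuous abstinence and give no rate, and half of full power is lost only if f is below about one third or if the sampling arm quits later. Both are assumptions.

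*Some participants will pass.* True. A quit date is encouraged without fixed timing, and immediate quitting is not discouraged. Sources of Materials even places intake at the screening appointment. Those who stop at once and stay stopped are successes. The defect is confined to delayed quitters.

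*Any grace length is arbitrary.* True. Someone who quits for good in month 2 still fails a one-month grace definition. That is a reason to show both definitions, not to omit the grace period.

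A reader might also infer that quit attempts must be added as an outcome, since Specific Aims speaks of an intervention "to enhance patient motivation to make and succeed in a quit attempt". The documents do not require it: they state that the primary outcome here is abstinence, in contrast to an earlier sampling trial powered on quit attempts. Nor could quit attempts simply be read off the calendar. It records tobacco use, not intent, and any smoking in 30 days qualifies for entry, so a non-daily smoker's ordinary smoke-free day could count.

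**Conclusion.** The point holds as a defect in a secondary-outcome definition. As written, continuous abstinence starts before some participants are randomised or have NRT, allows no delay, and scores lasting delayed quitters as failures at all three time points. It measures immediate, sustained quitting, which the intervention does not ask for.

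The size of the effect on power cannot be computed from the documents. Under the equal-f assumption it ranges from no loss (95%) to 17% power as f goes from 1 to 0.1, and lower still if the sampling arm quits later. The primary outcome and the GEE analysis are untouched, so the trial's main conclusion is not at risk. The change is worth making because this is the plan's only proportion that measures sustained quitting and the data for a better definition are already planned.

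**What to change.** In Statistical Analysis:

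1. Anchor the outcome at randomisation, which every participant has, instead of lung screening.
2. Define sustained abstinence with a pre-specified grace period up to the month-1 visit: no smoking on the daily calendar from month 1 to Week 12, and from month 1 to Week 26, with CO confirmation at the later visit.
3. Keep the no-grace definition from randomisation as a strict sensitivity analysis at Weeks 12 and 26. Report Week 4 under the strict definition only, since the grace period covers that interval.
4. State in the plan that strict continuous abstinence reflects immediate quitting and that the trial was not powered for it.

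The cost is two derived variables from the planned calendar and CO tests; there is no new data collection and no change to treatment. The grace-period definition is less strict and its length is a convention, so both sets of results should be shown. A quit-attempt outcome is optional and is not part of this change.
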